#### 7.4.2. Dose Modifications

The summary of dose modifications will include:

- The frequency of subjects with at least 1 dose reduction
- The reason for dose reduction
- The frequency of subjects with at least 1 interruption of study drug
- The reason for interruption of study drug

Dose reduction is defined as a prescribed non-zero daily dose that is lower than the planned dose (200 mg daily). An interruption of study drug is defined as a prescribed daily dose of 0 mg.

The reason for an interruption of study drug or dose reduction will be derived based on the "Reason for prescribed dose change" in the "Prescribed Dose" eCRF.

## 7.5. Concomitant Therapies

The following summaries will be presented by treatment arm based on the safety analysis set for the Double-blind Period and the OLE analysis set for the OLE Period.

**Concomitant medications** are defined as non-study medications (from the "Prior and Concomitant Medications" eCRF) that are started during the on-treatment period or are started before the start of the study treatment and end or remain ongoing during the on-treatment period.

All non-study medications will be coded according to ATC code and PT using the latest version of the WHO Drug Dictionary. All concomitant medications will be summarized in frequency tabulations according to WHO ATC third level and PT.

**Concomitant procedures** are defined as procedures (from the "Prior and Concomitant Procedures" eCRF) that are started during the on-treatment period or are started before the start of the study treatment and end or remain ongoing during the on-treatment period.

The concomitant procedures will be coded by the latest version of MedDRA by SOC and PT and will be summarized in frequency tabulations by SOC and PT.

Concomitant medications and concomitant procedures will be provided in by-subject listings.

## 7.6. Efficacy Analyses

The following analyses will be based on the FAS using the IXRS randomization stratification factors, unless otherwise specified. The efficacy analyses will include all data from the Double-blind Period. For subjects who discontinue treatment or become unblinded prior to completion of the 24-week Double-blind Period, their efficacy data prior to start of the OLE Period will be included in this evaluation based on the ITT principle.

## 7.6.1. Primary Endpoint (Hb Response)

The primary endpoint is Hb response, defined as a  $\geq 1.0$  g/dL increase in average Hb concentration from Week 12 through Week 24 compared with baseline (defined in Section 6.3.4.1).

Hb concentrations assessed within 8 weeks after an RBC transfusion will be excluded from the analysis of the primary endpoint. Subjects who do not have at least 2 on-treatment Hb concentration assessments from Week 12 to Week 24 will be considered non-responders.

## 7.6.1.1. Primary Analyses

The primary endpoint of Hb response will be tested using the Mantel-Haenszel stratum weighted method adjusting for randomization stratification factors. The proportion of subjects who achieved a Hb response will be summarized for each treatment arm. The adjusted difference in Hb response rate between the mitapivat arm and placebo arm, along with the 95% CI and the 2-sided p-value, will be provided.

In addition, for subjects who achieve an Hb response, mean Hb concentration increase and duration of Hb response will be summarized by treatment arm. For subjects who achieve Hb response, duration of Hb response will be calculated as the number of days from start of Hb response through the date of loss of Hb response, where:

- Start of Hb response is defined as the earliest date on or after the 'reference date' (as defined in Section 6.3.4.1) with Hb change from baseline  $\geq 1.0 \text{ g/dL}$
- Loss of Hb response is defined to have occurred on the first date with Hb change from baseline <1.0 g/dL after the last assessment with Hb change from baseline  $\ge 1.0 \text{ g/dL}$

• For subjects who do not have loss of Hb response, the duration of Hb response will be censored at the end of the 24-week Double-blind Period.

#### 7.6.1.2. Sensitivity Analyses

The following sensitivity analyses will be performed:

- Hb response will be summarized using the methodology described for the primary analysis but based on PPS.
- Hb response will be analyzed using the methodology described for the primary analysis but including only those subjects who completed 24 weeks of study treatment and who did not receive any concomitant medications (prior to completion of 24 weeks of study treatment) that could affect the Hb concentrations. The list of associated concomitant medications will be finalized prior to the database lock and unblinding of the study for the primary analysis.

## 7.6.2. Key Secondary Endpoints

# 7.6.2.1. Change from Baseline in Average FACIT-Fatigue Subscale Score from Week 12 through Week 24

The FACIT-Fatigue subscale includes a 13-item self-reported fatigue subscale, which assesses the severity and impact of fatigue (including the impact on daily activities and functioning). The subscale has a 7-day recall period and is scored on a 5-point scale: 0 (not at all) to 4 (very much). The total FACIT-Fatigue subscale score ranges from 0 to 52, with a higher score indicating better HRQOL. FACIT-Fatigue subscale scores within 8 weeks after an RBC transfusion will be excluded from the analyses described below.

The primary analysis for change from baseline in average FACIT-Fatigue subscale score from Week 12 through Week 24 will be based on an analysis of covariance (ANCOVA) with treatment arm as the independent variable, and covariates for randomization stratification factors and baseline FACIT-Fatigue subscale score. Treatment effect will be evaluated as a contrast of mitapivat versus placebo. The least square (LS) means will be presented by treatment arm and the LS mean for the treatment difference between mitapivat and placebo will be presented with the associated 95% CI and 2-sided p-value.

The frequency of subjects with each response level will be summarized by treatment arm and study visit. The total subscale score will be summarized by treatment arm and study visit.

The following sensitivity analyses will also be performed:

• Mixed-effect Model for Repeated Measures (MMRM)

The change from baseline in average FACIT-Fatigue subscale score from Week 12 through Week 24 will be compared between the mitapivat arm and the placebo arm by the MMRM method. The model will include change from baseline in FACIT-Fatigue subscale score as the dependent variable; baseline FACIT-Fatigue subscale score as a covariate, treatment, visit, and treatment-by-

visit interaction as fixed factors; and subject as the random effect with adjustment for the randomization stratification factors.

The MMRM model will be based on the restricted maximum likelihood method assuming an unstructured covariance structure to model the within-subject errors. If the model does not convergence, the compound symmetry structure will be used instead. A Kenward-Roger approximation will be used for the denominator degrees of freedom.

The estimated treatment difference between the mitapivat arm and the placebo arm in the change from baseline in average FACIT-Fatigue subscale score from Week 12 through Week 24 based on the LS Means will be provided with 95% CI and the 2-sided p-value. The estimated change from baseline for each treatment arm and the estimated treatment difference at each visit will be provided with 95% CI. Two-sided p-values will be provided for the estimated treatment difference at each visit.

- To assess the durability of effect of the study treatment and longitudinal trending, the FACIT-Fatigue score changes from baseline at each planned visit starting from Week 12 (ie, Week 12, Week 16, Week 20, Week 24) will be summarized using an ANCOVA model as described for the primary analysis.
- Pattern-mixture model with control-based pattern imputation for missing data

Missing FACIT-Fatigue data will be imputed using multiple imputation methodology (Rubin, 1987) by replacing each missing value with a set of plausible values that represent the uncertainty about the correct value to impute. A Markov Chain Monte Carlo (MCMC) method will first be used to generate data sets following monotone missing patterns, and a regression-based patternmixture method will then be used to impute the remaining missing values based on the distribution data from the subjects in the placebo arm. This conservative approach assumes that after discontinuation from study treatment, subjects in the mitapivat arm will exhibit the same future evolution of the disease as subjects in the placebo arm; this approach will tend to move the estimate of the treatment effect toward a smaller value compared with missing-at-random-based analysis methods, such as mixed models with repeated measures or standard multiple imputation models. The same ANCOVA model as described for the primary analysis will be used on each of the multiply-imputed datasets and the statistics will be combined according to Rubin's rules (Rubin, 1987).

#### 7.6.2.2. Change from Baseline in Average Hb Concentration from Week 12 through Week 24

The change from baseline in average Hb concentrations from Week 12 through Week 24 will be analyzed using an ANCOVA with treatment arm as the independent variable, and covariates for randomization stratification factors and baseline Hb concentration. Treatment effect will be evaluated as a contrast of mitapivat versus placebo. The LS means will be presented by treatment arm and the LS mean for the treatment difference between mitapivat and placebo will be presented with the associated 95% CI and 2-sided p-value.

A sensitivity analysis for change from baseline in average Hb concentrations from Week 12 through Week 24 will be performed based on the MMRM method as described in Section 7.6.2.1.

Hb concentrations assessed within 8 weeks after an RBC transfusion will be excluded from these analyses.

## 7.6.3. Additional Secondary Efficacy Endpoints

#### 7.6.3.1. Hb 1.5+ Response

Hb 1.5+ response is defined as a  $\geq$ 1.5 g/dL increase in average Hb concentration from Week 12 through Week 24 compared with baseline (defined in Section 6.3.4.1).

Hb concentrations assessed within 8 weeks after an RBC transfusion will be excluded from the analysis of this endpoint. Subjects who do not have at least 2 on-treatment Hb concentration assessments from Week 12 to Week 24 will be considered non-responders.

Hb 1.5+ response will be summarized using the Mantel-Haenszel stratum weighted method adjusting for randomization stratification factors. The proportion of subjects who achieved a Hb 1.5+ response will be summarized for each treatment arm. The adjusted difference in Hb 1.5+ response rate between the mitapivat arm and placebo arm, along with the 95% CI will be provided.

# 7.6.3.2. Change from Baseline in Markers of Hemolysis and Erythropoiesis at Week 24

Markers of hemolysis include indirect bilirubin, LDH, and haptoglobin. Markers of erythropoiesis include reticulocytes and erythropoietin.

Values and changes from baseline will be summarized based on descriptive statistics, by treatment arm and study visit, through Week 24 of the Double-blind Period. Change from baseline to Week 24 will be compared between treatment arms following the same methodology as described in Section 7.6.2.2.

By-subject longitudinal plots will be presented with values at baseline and postbaseline, transfusions, and prescribed dose over time. The plots will further include Hb response status, treatment arm, age, sex, race, randomization stratification factors, 24-week baseline transfusion burden, and hydroxyurea status.

## 7.6.3.3. PGIS-Fatigue and PGIC-Fatigue

The PGIS and PGIC questions are patient-reported prospective and retrospective ratings, respectively, of disease-related concepts or overall status. The PGIS is a validated, singleitem measure used to assess the HRQOL impact or severity of a specific health condition (US FDA, 2018; Viktrup et al, 2012). The PGIC is a validated, single-item measure used to assess the change over time in a concept or overall status (Guy, 1976; US FDA, 2018). The PGIS questions will be administered to assess severity (on a 4-point scale ranging from "None" to "Severe") of the following 3 concepts as perceived by the subject over the recall periods noted below:

• Fatigue (7-day recall)

Similarly, the PGIC questions will be used to assess subject-perceived change compared with baseline in the same concepts on a 5-point scale ranging from "Much better" to "Much worse."

Assessments within 8 weeks after an RBC transfusion will be excluded from the analysis of the PGIS-Fatigue and PGIC-Fatigue endpoints.

The frequency of subjects with each response level of PGIS-Fatigue and PGIC-Fatigue will be summarized by treatment arm and study visit. Missing data will also be summarized.

A subject will be considered to have met the PGIS-Fatigue endpoint at Weeks 12, 16, 20, or 24 (improvement in PGIS-Fatigue by at least 1 category at the corresponding visit week compared with baseline, or "no change" if no or mild fatigue at baseline) if the severity at baseline compared to post-baseline (at the corresponding study visit) meets one of the following:

- None (baseline) -> None (post-baseline)
- Mild -> Mild or None
- Moderate -> Mild or None
- Severe -> Moderate, Mild or None

At each of Week 12, 16, 20 and 24 visits, the PGIS-Fatigue endpoint will be compared between the mitapivat arm and the placebo arm using the Mantel-Haenszel stratum weighted method adjusting for randomization stratification factors. The proportion of subjects who achieved the PGIS-Fatigue endpoint will be summarized for each treatment arm and study visit. The adjusted difference in the proportion of subjects who met the PGIS-Fatigue endpoint between the mitapivat arm and placebo arm, along with the 95% CI will be provided for each study visit.

A subject will be considered to have met the PGIC-Fatigue endpoint at Weeks 12, 16, 20, or 24 (improvement PGIC-Fatigue or "no change" if no or mild fatigue at baseline as assessed by PGIS-Fatigue) if the subject-perceived change compared with baseline meets one of the following at the corresponding study visit

- PGIS at baseline is None or Mild and PGIC is "No Change", "A Little Better", or "Much Better"
- PGIS at baseline is Moderate or Severe and PGIC is "A Little Better" or "Much Better"

At each of Week 12, 16, 20 and 24 visits, the PGIC-Fatigue endpoint will be compared between the mitapivat arm and the placebo arm using the Mantel-Haenszel stratum weighted method adjusting for randomization stratification factors. The proportion of subjects who achieved the PGIC-Fatigue endpoint will be summarized for each treatment arm and study visit. The adjusted difference in the proportion of subjects who met the PGIC-Fatigue

endpoint between the mitapivat arm and placebo arm, along with the 95% CI will be provided for each study visit.

## 7.6.3.4. Change from Baseline in the 6MWT Distance at Week 24

The 6MWT is a well-established performance outcome (PerfO) measure that is widely used to evaluate physical activity in terms of distance walked in patients with a variety of conditions. The test measures the distance an individual can walk on a hard, flat surface in 6 minutes. A lower score, based on less distance covered in 6 minutes, indicates worse level of physical activity.

Values and changes from baseline will be summarized based on descriptive statistics, by treatment arm and study visit, through Week 24 of the Double-blind Period. Change from baseline to Week 24 will be compared between treatment arms following the ANCOVA methodology as described in Section 7.6.2.2.

## 7.6.3.5. Changes from Baseline in Markers of Iron Metabolism at Week 24

Iron metabolism will be assessed based on serum ferritin and transferrin saturation.

Values and changes from baseline will be summarized based on descriptive statistics, by treatment arm and study visit, through Week 24 of the Double-blind Period. Change from baseline to Week 24 will be compared between treatment arms following the ANCOVA methodology as described in Section 7.6.2.2.

By-subject longitudinal plots will be presented with values at baseline and postbaseline, transfusions, and prescribed dose over time. The plots will further include Hb response status, treatment arm, age, sex, race, randomization stratification factors, 24-week baseline transfusion burden, and hydroxyurea status.

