4.1.2. Double-blind Period

Eligible subjects will be randomly assigned in a 2:1 ratio to receive study drug (mitapivat or placebo) for BID oral administration. Randomization will be stratified by baseline Hb concentration and thalassemia genotype (see Section 6.3.1). Study subjects, Investigators, clinical study center personnel, and the Sponsor will be blinded to the subject's treatment assignment (see Section 6.3.2). Subjects will receive either mitapivat or matched placebo for 24 weeks. Study visits will occur approximately every 4 weeks for efficacy and safety assessments. If allowed by local institutional guidelines, subjects will have the option for at-home study visits as designated in the Schedules of Assessments. Subjects who discontinue study drug before completing the Double-blind Period are not permitted to receive mitapivat in the Open-label Extension Period.

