# 6. GENERAL STATISTICAL CONSIDERATIONS

## 6.1. Randomization, Blinding, and Unblinding

Eligible subjects will be randomized in a 2:1 ratio to mitapivat or matched-placebo.

Randomization assignment will be implemented by an interactive voice/web response system (IXRS) and stratified by:

- Baseline Hb concentration ( $\leq 9.0 \text{ g/dL}$  or 9.1-10.0 g/dL)
- Thalassemia genotype (α-thalassemia/HbH disease or β-thalassemia)

This study includes a Double-blind Period followed by an OLE Period. Study subjects, Investigators, clinical study center personnel, pharmacists, and the Sponsor will be blinded to the subject's treatment assignment. After completing the Double-blind Period, subjects will be provided the opportunity to receive mitapivat in the OLE Period. At the last study visit of the Double-blind Period, subjects who continue in the OLE Period will be provided with active mitapivat; however, study subjects, Investigators, clinical study center personnel, and the Sponsor will continue to remain blinded to the randomized treatment assignment during the previous Double-blind Period until the study is unblinded for the analysis of the primary endpoint.

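### The PGIS-Fatigue and PGIC-Fatigue comparisons (SAP 7.6.3.3) do not adjust for baseline PGIS, which sets each subject's bar for success; the intervals are valid but may be wider than needed

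*SAP*

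**What the plan says.** SAP 7.6.3.3 defines two yes/no fatigue endpoints, each read at Weeks 12, 16, 20 and 24. For the first, "the PGIS-Fatigue endpoint will be compared between the mitapivat arm and the placebo arm using the Mantel-Haenszel stratum weighted method adjusting for randomization stratification factors". For the second, "the PGIC-Fatigue endpoint will be compared between the mitapivat arm and the placebo arm using the Mantel-Haenszel stratum weighted method adjusting for randomization stratification factors". Planned output is an adjusted difference with a 95% CI at each visit; no p-value is named.

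The factors in question are two. Protocol 4.1.2 says "Randomization will be stratified by baseline Hb concentration and thalassemia genotype", and SAP 6.1 gives two levels of each, so there are 4 strata. Baseline PGIS is not among them.

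The success rules depend on baseline PGIS. A subject with mild fatigue succeeds under "Mild -> Mild or None", so staying put counts. A subject with moderate fatigue succeeds only under "Moderate -> Mild or None", so staying put is a failure. The PGIC rule has the same cut: above it, success requires "PGIS at baseline is Moderate or Severe and PGIC is 'A Little Better' or 'Much Better", whereas a rating of no change is enough for a subject with no or mild baseline fatigue.

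By contrast, the FACIT-Fatigue analysis in SAP 7.6.2.1 uses "covariates for randomization stratification factors and baseline FACIT-Fatigue subscale score".

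**The concern.** A baseline variable that decides whether an unchanged subject is a success or a failure is a natural candidate for adjustment. Here it is measured before the first dose: the protocol's Schedule of Assessments places PGIS on Day 1 and exempts only PGIC. It is nevertheless left out of the comparison.

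Two things are at stake. Variation in outcome that baseline PGIS could explain stays in the error term, so the interval may be wider than it has to be. And because randomization does not balance baseline fatigue, a chance difference between 114 and 57 subjects feeds into the estimated treatment difference. The same imbalance would then recur at all four visits and in both endpoints.

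**Working it through.** **Inputs.** Arm sizes of 114 and 57 (SAP 6.2.1), 2:1 allocation in 4 strata (SAP 6.1), and the success rules of SAP 7.6.3.3. The documents give neither the baseline PGIS distribution nor any PGIS or PGIC success rate. Every rate below is therefore an assumption.

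**1. The plan's own figures.** No power or precision is stated for these two endpoints. The sample size itself reproduces:
- Hb response, 10% versus 35%: pooled rate (114×0.35 + 57×0.10)/171 = 0.267; null SE 0.0717, alternative SE 0.0598; (0.25 − 1.96×0.0717)/0.0598 = 1.83, power 96.6% (stated 95%).
- FACIT-Fatigue, difference 5.5, SD 12: SE = 12×√(1/114 + 1/57) = 1.947; 5.5/1.947 − 1.96 = 0.865, power 80.7% (stated 80%).

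**2. Why baseline PGIS should predict success.** Success is 1 − P(worsen) for none/mild and P(improve) for moderate/severe. If movement probabilities are similar in the two groups, the gap is 1 − P(worsen) − P(improve) = P(unchanged). Baseline PGIS then predicts success to the extent that subjects stay in their category.

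**3. Chance imbalance.** With half the subjects moderate/severe, the SD of the arm difference in that share is √(0.25×(1/114 + 1/57)) = 0.081. One SD moves the unadjusted difference by 0.081 × gap, if the gap is the same in both arms:
- gap 55 points: 4.5 points
- gap 45 points: 3.6 points (about 7 points at the 95% limit)
- gap 25 points: 2.0 points

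**4. Standard error, large-sample formula.** Take placebo success of 85% (none/mild) and 30% (moderate/severe), half in each group, and gains of 10 and 20 points on mitapivat (95% and 50%).
- Total variances: placebo 0.575×0.425 = 0.2444; mitapivat 0.725×0.275 = 0.1994. SE without baseline PGIS = √(0.1994/114 + 0.2444/57) = 0.0777.
- Within-group variances: placebo (0.1275 + 0.2100)/2 = 0.1688; mitapivat (0.0475 + 0.2500)/2 = 0.1488. SE with baseline PGIS = √(0.1488/114 + 0.1688/57) = 0.0653.
- Ratio 0.84. This is an upper limit on the gain, because it ignores thin strata and the unequal effect in the two groups.

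**5. Standard error, simulation.** Trials of 171 subjects, 2:1 within the 4 randomization strata, no missing data, Mantel-Haenszel difference with Sato variance, 4 strata (as planned) against 8 (crossed with baseline PGIS group):

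| Placebo success, none/mild and moderate/severe | Share moderate/severe | Gain on mitapivat, points | Change in mean SE |
|---|---|---|---|
| 85%, 30% | 50% | 5 and 25 | about −10% |
| 85%, 30% | 50% | 10 and 20 | about −14% |
| 80%, 40% | 50% | 5 and 25 | about −4% |
| 75%, 50% | 40% | 10 and 20 | about −1% |
| 60%, 60% (not prognostic) | 50% | 15 and 15 | about +1% |

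**6. A second set of assumptions.** Here the share of placebo subjects who stay in their category is varied, with 30-70% none/mild at baseline. The CI width is multiplied by about 0.84-0.87 if 60% stay (for example 0.311 to 0.261), 0.94-0.96 if 40% stay, and 0.99-1.00 if 20% stay.

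**7. Validity.** Coverage of the planned interval was about 94-95%. With no treatment effect, the interval excluded zero equally often with 4 or 8 strata (5.9% each).

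**The case against.** The strongest reply is that nothing here is an error. The planned interval has its nominal coverage, and chance imbalance in an unadjusted factor is part of the sampling variation that the interval already covers. That stands. A reader might infer that omitting baseline PGIS biases the comparison or inflates type I error; step 7 shows that it does neither.

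A reader might also infer that the trial loses power for a formal test. The fixed sequence in SAP 6.2.1 contains only Hb response, FACIT-Fatigue and average Hb, and only a difference and a 95% CI are planned here. For that reason the effect is given as a standard error and not as power.

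Nor do the documents support calling baseline PGIS a strong predictor. The definition fixes the bar, not the strength of prediction. If few subjects stay in their category the gap closes, and regression to the mean would also narrow it. A subject starting at none must stay at none. No separate PGIC scenario was simulated, so for that endpoint the result carries over by the shared rule only.

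Two further points are fair but do not settle the matter. The plan is consistent in that its other binary endpoints (Hb response and Hb 1.5+) use the same method and factors; but for those, success is not defined by a different rule in each baseline group. And Protocol 10.4.3.2.4 plans proportions separately for the none/mild and moderate/severe baseline groups, which would show an imbalance. The SAP does not repeat that split, and a descriptive display does not adjust the overall difference.

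**Conclusion.** The point holds as a cheap improvement in precision. SAP 7.6.3.3 leaves out of both comparisons the one baseline variable that its own definitions use to set the bar. The planned 95% CI is valid, may be wider than needed, and leaves the estimate exposed to chance imbalance in baseline fatigue.

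The size cannot be fixed from the documents. Under the assumptions shown, the change in standard error runs from a reduction of 10-14%, when placebo success differs strongly by baseline group, through about 4% and about 1% for weaker gaps, to an increase of about 1% if baseline PGIS is not prognostic. The possible gain is much larger than the possible loss. No formal test or trial conclusion depends on it.

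**What to change.** In SAP 7.6.3.3, before unblinding, add baseline PGIS-Fatigue group (none/mild versus moderate/severe) as a stratum in the Mantel-Haenszel comparison for both PGIS-Fatigue and PGIC-Fatigue at Weeks 12, 16, 20 and 24, alongside baseline Hb and genotype. Two levels match the cut in the success rules; all four PGIS categories would give 16 strata, too thin for 57 placebo subjects to be attractive.

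The cost is one sentence and 8 strata instead of 4. Some will be sparse: if the smallest randomization stratum holds 30% × 30% of subjects and 30% of those are moderate/severe, it expects 57×0.027 = 1.5 placebo subjects and has none with probability 0.973^57 = 0.21. A stratum with subjects in only one arm gets zero weight; here that would drop about 114×0.027 = 3 mitapivat subjects, a small loss. Assessments missing or excluded after transfusion would thin the strata a little more. A subject without a baseline PGIS cannot be classified on either endpoint, so the added stratum need exclude nobody further; the sentence should say how such a subject is handled.
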